3.5.2. Data Handling for Efficacy and Safety Endpoints

- If there is a significant degree of non-normality for a continuous endpoint, analyses may be performed on log-transformed data or using nonparametric methods, as appropriate.
- Analyses will be descriptive in nature and formal comparisons of outcomes between treatment groups are not planned.

3.5.3. Data Handling for Laboratory data

Laboratory data that are continuous in nature but are less than the lower limit of quantitation or above the upper limit of quantitation will be imputed as follows:

- A value that is 1 unit less than the limit of quantitation will be used for calculation of descriptive statistics if the data is reported in the form of "< x" (x is considered the limit of quantitation). For example, if the values are reported as < 50 and < 5.0, then values of 49 and 4.9 will be used for calculation of summary statistics, respectively. However, for direct bilirubin, a value of "< 0.1" will be treated as 0.05 for calculation of summary statistics.
- A value that is 1 unit above the limit of quantitation will be used for calculation of descriptive statistics if the data is reported in the form of "> x" (x is considered the limit of quantitation). For example, if the values are reported as > 50 and > 5.0, then values of 51 and 5.1 will be used for calculation of summary statistics, respectively.
- The limit of quantitation will be used for calculation of descriptive statistics if the data is reported in the form of " $\leq x$ " or " $\geq x$ " (x is considered as the limit of quantitation).

3.6. Visit Windows

3.6.1. Analysis Windows

When applicable, the nominal visit as recorded on the eCRF will be used. For parameters assessed at the end of treatment (EOT) visit, the assessment results will be assigned to the next scheduled visit where the respective data were scheduled to be collected for summary. Unscheduled scans will be used for determination of the time-to-event and tumor response efficacy endpoints.

For data collected after unblinding of the study, nominal visit may no longer be applicable. In such case, summary by visit will be based on the following visit windows as described in Table 3-2.

Start (day)	Stop (day)	Scheduled Visit day	Week
1	1	1	0
2	21	15	2
22	35	29	4
36	49	43	6
:	:	:	:
7*(X-1)+1	7*(X+1)	X*7+1	Х

Table 3-2.	Analysis Visit Window
	1 kindly sis visit villaov

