Clinic/laboratory visits will occur every 2 weeks for the first 12 weeks, every 4 weeks between Weeks 12 and 24, and every 6 weeks between Weeks 24 and 48. Subjects continuing on study drug past Week 48 will have clinic visits every 12 weeks. Subjects will be assessed for safety at each visit. Subjects will be assessed for CLL disease status by physical and laboratory examinations at each visit and by CT or MRI at Weeks 8, 16, 24, 36, and 48 and every 12 weeks thereafter. As of Amendment 9, Version 10, CT/MRI assessments will no longer be performed at the every 12 week scheduled visits, and will only be performed at the time of clinically-suspected disease progression or at study discontinuation.

Following unblinding of the study:

- Subjects who were randomized to idelalisib on Study GS-US-312-0116 and who received ≥ 24 weeks idelalisib will complete Visit 16+ twelve weeks from the date of their last radiology assessment (CT/MRI) and study visits will continue every 12 weeks thereafter. Visits 3 through 15 will not be required.
- Subjects who have received < 24 weeks idelalisib will have all Study GS-US-312-0117 assessments completed per the Schedule of Procedures until they have received idelalisib for 24 weeks cumulative across both studies. After completion of 24 weeks of cumulative idelalisib treatment, Visit 16+ will be conducted 12 weeks from the date of their last radiology assessment (CT/MRI), after which time study visits will occur every 12 weeks.

Test Therapy, Dose, and Mode of Administration:

Blinded Portion

- Arm A: Idelalisib, 300 mg/dose BID starting on Day 1 and administered continuously thereafter; the study drug will be provided as 2 tablets of active idelalisib for oral administration
- Arm B: Idelalisib, 150 mg/dose BID starting on Day 1 and administered continuously thereafter; the study drug will be provided as 1 tablet of active idelalisib and 1 tablet of placebo for oral administration

Open-Label Extension Portion (following unblinding)

- Arm A: subjects already on 300 mg BID will continue, and newly enrolled subjects will receive 150 mg BID
- Arm B: subjects already on 150 mg BID will continue, and newly enrolled subjects will receive 150 mg BID

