6.2.15. Visit 15 and Subsequent Visits (Day 337 and Every 12 Weeks) (Clinic and Radiology Visits)

The procedures outlined in Table 6-15 will be performed at Visit 15 (Day 337 [±3 days]) and every 12 weeks thereafter [±7 Days]).

Table 6-15. Procedures and Assessments at Visit 15 and Subsequent Visits (Day 337 and Every 12 Weeks)

Assessment or Procedure	Explanation	
Pre-Visit Tumor Assessmen	Pre-Visit Tumor Assessment	
Radiology assessment ^a	CT or MRI imaging of neck, chest, abdomen, and pelvis within 1 week prior to the visit; the assessment should be done even if study drug has been interrupted.	
During-Visit Procedures an	nd Assessments	
FACT-Leu	HRQL instrument (Appendix 2) to be administered before any other procedures are performed and before any study-related information is communicated to the subject	
EQ-5D	Health utility instrument (Appendix 4) to be administered after FACT-Leu but before any other procedures are performed and before any study-related information is communicated to the subject	
Adverse events	Recording of adverse events occurring since prior visit	
Concomitant medications	Recording of concomitant medication used since prior visit	
Study drug return/accounting	Counting returned study drug.	
Performance status	Using Karnofsky performance status criteria (see Appendix 3)	
Oxygen saturation	To be assessed by pulse oximetry while subject is breathing room air	
Physical examination	Including weight, evidence of palpable lymphadenopathy, hepatomegaly, and/or splenomegaly	
Urine β-HCG dipstick	For women of child-bearing potential only	
Hematology	Including hematocrit, hemoglobin, erythrocyte count; absolute counts of leukocytes, neutrophils, lymphocytes, monocytes, eosinophils, basophils, platelet count	
Serum chemistry	Including sodium, potassium, chloride, glucose, urea, creatinine, calcium, phosphorus, total protein, albumin, ALT, AST, ALP, GGT, total bilirubin, LDH, uric acid, cholesterol, triglycerides	
CMV viral load	CMV viral load testing approximately every 4 weeks throughout the course of idelalisib treatment	
Circulating cells	Including cells for analysis of PI3K/AKT/mTOR pathway activation and quantitation of absolute number of CD4+, CD5+, CD8+, CD16/CD56+, CD19+, and CD+20 cells by flow cytometry	
Immune monitoring	Lymphocyte subset panel using flow cytometry (immunophenotyping), serum CH50 level	
Biomarkers	Collection of plasma and serum for evaluation of circulating chemokines and cytokines	

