	 5) Willingness and ability to comply with scheduled visits, drug administration plan, imaging studies, laboratory tests, other study procedures, and study restrictions. Note: Psychological, social, familial, or geographical factors that might preclude adequate study participation should be considered. 6) Evidence of a personally signed informed consent indicating that the subject is aware of the neoplastic nature of the disease and has been informed of the procedures to be followed, the experimental nature of the therapy, alternatives, potential benefits, possible side effects, potential risks and discomforts, and other pertinent aspects of study participation.
Study Periods/Phases	Clinic/laboratory visits will occur every 2 weeks for the first 12 weeks, every 4 weeks between Weeks 12 and 24, and every 6 weeks between Weeks 24 and 48. Subjects continuing on study drug past Week 48 will have clinic visits every 12 weeks. Subjects will be assessed for safety at each visit. Subjects will be assessed for CLL disease status by physical and laboratory examinations at each visit and by CT or MRI at Weeks 8, 16, 24, 36, and 48 and every 12 weeks thereafter.
	 Following unblinding of the study: Subjects who were randomized to idelalisib on Study GS-US-312-0116 and who received ≥ 24 weeks idelalisib will have Visit 16+, conducted 12 weeks from the date of their last radiology assessment (CT/MRI) and study visits will continue every 12 weeks thereafter. Visits 3 through 15 will not be required. Subjects who have received < 24 weeks idelalisib will have all Study GS-US-312-0117 assessments completed per the Schedule of Procedures until they have received idelalisib for 24 weeks cumulative across both studies. After completion of 24 weeks of cumulative idelalisib treatment, Visit 16+ will be conducted 12 weeks from the date of their last radiology assessment (CT/MRI), after which time study visits will occur every 12 weeks.

Schedule of Assessments

The schedule of assessments is located in Appendix 2 of this statistical analysis plan (SAP).

Treatment Assignment	 Assignment to Arm A or Arm B with allocation based on the original primary study randomization Implementation through an interactive web response system (IWRS) 	
Site and/or Stratum Enrollment Limits	Approximately 90 centers in the United States and in Europe.	

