As a baseline, the last value obtained prior to the baseline reference date for efficacy endpoints, as defined in Section 3.5.1, will be used. The mean and change from baseline in mean scores to each subsequent assessment will be summarized for the subscale and composite scores. The best change from baseline during the study, defined as the highest positive value among all post-baseline visits minus the baseline value, will also be summarized.

Each subject's FACT-Leu subscales (ie, PWB, EWB, SWB, and FWB) scores at each assessment will be compared to their baseline scores. The minimally important difference (MID) for these subscales is 3 points {26297}. An increase of at least 3 points will be required as a definition of symptom improvement. The cumulative distribution function (CDF) of best change from baseline will be provided. For the MID improvement comparison, subjects with baseline score > 55 will be excluded (ie, subjects with no room for improvement). Time to symptom response will be assessed by defining the first occurrence of symptom improvement as an event. Subjects who do not experience a symptom improvement compared to baseline will be censored at their last available FACT-Leu assessment time.

A data listing for each individual item, the subscale scores, and the composite scores will be presented for each subject at each time point.

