7.2.1. Summaries of Numeric Laboratory Results

Descriptive statistics (sample size, mean, StD, median, Q1, Q3, minimum and maximum) will be provided for each laboratory test specified in the study protocol as follows:

- Baseline values
- Values at each post-baseline visit
- Change from baseline at each post-baseline visit

In the case of multiple values in an analysis window, data will be selected for analysis as described in Section 3.6.2. In addition, mean change from baseline (\pm standard error) and median (\pm Q1/Q3) for selected lab parameters will be plotted over time by treatment groups.

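### Table 3-2 keeps 14-day windows in the 12-weekly post-unblinding phase, so by-visit summaries can split one visit round across several sparse time points

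*SAP*

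**What the plan says.** SAP 3.6.1 uses the visit label recorded on the eCRF where it applies. It then states: "For data collected after unblinding of the study, nominal visit may no longer be applicable". For those records: "In such case, summary by visit will be based on the following visit windows as described in Table 3-2". Table 3-2 lists Weeks 0, 2, 4 and 6 and then a general row: start Day 7(X-1)+1, stop Day 7(X+1), scheduled Day 7X+1. It does not say which values X takes, and it gives no wider window for later follow-up.

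The visit schedule after unblinding is in SAP 1.2. Subjects randomized to idelalisib who have had at least 24 weeks of it have Visit 16+ "conducted 12 weeks from the date of their last radiology assessment (CT/MRI) and study visits will continue every 12 weeks thereafter", with Visits 3 to 15 dropped. Subjects with less than 24 weeks have "assessments completed per the Schedule of Procedures until they have received idelalisib for 24 weeks cumulative across both studies", and then also move to 12-weekly visits counted from their last scan.

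Analysis days run on another clock. Under SAP 3.5.1 and Table 3-1, Day 1 for the pooled Arm A group is primary-study randomization (efficacy) or first idelalisib dose (safety). For the placebo crossovers it is the first idelalisib dose.

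By-visit output is planned for laboratory data (SAP 7.2.1: "Change from baseline at each post-baseline visit"), for FACT-Leu (SAP 6.1.2.9: "The mean and change from baseline in mean scores to each subsequent assessment will be summarized"), for Karnofsky and EQ-5D, and in the over-time figures of SAP Appendix 1.

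**The concern.** A 12-weekly subject contributes about one visit to every six consecutive two-week windows. Which window receives it depends on that subject's last scan date relative to Day 1, and nothing in the SAP aligns the two. Where scan dates are scattered, neighbouring time points in a table or figure hold different subjects, and each holds only part of the visit round. A step in the median hemoglobin or mean FACT-Leu curve could then come from a change in who is being averaged. The displays at stake are the long-term open-label time courses, which are a large part of what this SAP is written to produce.

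Because X is undefined, two programmers could also follow the table and produce different output: contiguous even-week windows, or isolated windows at scheduled weeks only.

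**Working it through.** **Reproducing the table.** The formula gives Day 22-35 (scheduled Day 29) for X = 4 and Day 36-49 (Day 43) for X = 6, both as printed. For X = 2 it gives Day 8-21; the table starts that row at Day 2 to close the gap after Day 1. The width is 7(X+1) - 7(X-1) = 14 days, or -7 to +6 days around the scheduled day.

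**Are visits lost?** With X running over even weeks, Week 36 is Day 246-259 and Week 38 starts at Day 260. The windows are contiguous and no visit is lost. With X limited to 12-weekly weeks, Week 48 starts at Day 330, so Days 260-329 are uncovered: 70 of 84 days, or 83%.

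**Visit tolerance.** Protocol 6.2.15 and Appendix 7 allow ±7 days for the 12-weekly visits. For X = 60 the scheduled day is 421 and the window is Day 414-427. A permitted visit on Day 428 falls in Week 62 under the even-week reading and in no window under the scheduled-week reading.

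**Share of a visit round in the matching window.** An 84-day cycle contains 84/14 = 6 two-week windows. The documents do not give the distribution of visit offsets within the cycle, so these are assumed scenarios, in whole days:

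- (a) Offsets uniform over the cycle: 14/84 = 16.7%.
- (b) Visits on the 12-week grid with uniform ±7-day variation: 14 of 15 days fall inside, 93%.
- (c) As (b), but the anchoring scan is 0 to 7 days before its visit (Protocol Table 6-15 allows up to one week): 91 of 120 combinations fall inside, 76%, with 23% in the preceding window.
- (d) Arm A transition at a random point in the scan cycle. The previous scan is reused if at most 28 days old (the four-week rule in Protocol 7.3); otherwise a new scan resets the anchor. Without visit variation, (29 + 7)/84 = 43%. With ±7-day variation, simulation of 600,000 visits gives 41% in the grid window, about 17% in each of three others, and 7% and 2% in the remaining two.

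| Scenario | In matching window | Uncovered if X is scheduled weeks only | Standard error relative to the full round, 1/√share |
|---|---|---|---|
| (a) uniform | 17% | 83% | 2.4 |
| (d) Arm A transition | 41% | 59% | 1.6 |
| (c) grid, scan 0-7 days early | 76% | 24% | 1.1 |
| (b) grid | 93% | 7% | 1.0 |

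Scenario (d) assumes that the primary study scanned on the same 12-week grid; its schedule is not in the documents. To illustrate scale, the 161 enrolled subjects would give at most 161/6 = 27 per window under (a), before division into treatment groups and before any attrition.

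**Who is likely to scatter?** Arm A subjects entered when the primary study stopped, at whatever study day they had reached, and SAP Appendix 2 puts their later imaging on standard of care. Placebo subjects who switched to open-label drug within the primary study while awaiting the amendment (SAP 3.5.1) have a Day 1 that precedes extension entry. By contrast, a crossover who starts idelalisib at entry is scanned "by CT or MRI at Weeks 8, 16, 24, 36, and 48 and every 12 weeks thereafter" (Protocol Synopsis, Study Procedures/Frequency), so later visits fall near Weeks 36, 48 and 60.

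**The case against.** A reader might infer that every post-unblinding time point holds one-sixth of the subjects, or that 67% to 83% of visits fall in no window. The documents support neither as a general statement.

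- One-sixth needs offsets spread evenly over 84 days. Protocol scans from Week 24 sit on a 12-week grid, and subjects who stay on it land mostly in the matching window. Even the Arm A transition scenario is uneven, at 2% to 41% per window.
- The 0, 2, 4, 6 rows read most naturally as contiguous even-week windows, which lose no visit. The 67% figure comes from 14-day windows on the 6-weekly schedule (28 of 42 days uncovered), but after unblinding subjects leave that schedule once they reach 24 cumulative weeks.
- Subjects below 24 cumulative weeks stay on the denser schedule, where two-week windows match the visits of the first 12 weeks. Two of the three presented groups are placebo crossovers.
- Table 3-2 applies only where the nominal visit does not.
- The analyses are descriptive with no formal comparisons (SAP 3.5.2), and continuous summary tables show the number with data, so sparse time points would be visible there.

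All of this stands, and it limits the size and reach of the problem. It does not remove it. Table 3-2 has no window fitted to 84-day visits, X is undefined, and the two clocks are not aligned. Nor can the nominal label be relied on: Protocol Appendix 7 notes that Visit 16+ may occur before Week 48 after unblinding, so that label does not fix a week.

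**Conclusion.** The concern holds as a mismatch between a stated windowing rule and the visit schedule. For post-unblinding records without an applicable nominal visit, 14-day windows can spread one 12-weekly round over up to six time points with different subjects in each, chiefly in Arm A subjects who transitioned at unblinding. How much it matters cannot be settled from the documents: the matching window holds about 17% of visits at the uniform extreme, about 41% in the assumed Arm A transition, and 76% to 93% on the grid. Outright loss of visits arises only if X means scheduled weeks. The one-day shortfall against the permitted +7-day visit needs no assumption about anchors.

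The effect is confined to by-visit descriptive displays. PFS, OS, DOR and response endpoints do not use these windows, nor do best-change or worst-grade summaries. This is a change that should be made, not one on which the main conclusions depend.

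**What to change.** In SAP 3.6.1 and Table 3-2:

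1. State which values X takes, and when a nominal visit counts as applicable.
2. For subjects still on the denser schedule through Week 24, keep nominal visits, or use the two-week windows up to Week 10 followed by midpoint windows: Week 12, Day 78-98; Week 16, Day 99-126; Week 20, Day 127-154; Week 24, Day 155-210.
3. For the 12-weekly phase use X = 36, 48, 60 and so on, with window Day 7(X-6)+1 to 7(X+6). Week 36 becomes Day 211-294 and Week 48 becomes Day 295-378. These windows are contiguous, 84 days wide, and cover every later visit whatever the anchor. Keep one record per subject per window under SAP 3.6.2.
4. Let records with a nominal Week 30 or Week 42 label keep it and stay out of the windows. Their target days, 211 and 295, are the first days of the Week 36 and Week 48 windows, so a one-day shift would otherwise change the assigned week.

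The cost is one table and the windowing program. Time resolution after Week 24 becomes coarser, which is the resolution of the visits themselves. Week 30 and Week 42 time points will contain only subjects with those nominal visits, and the tables should say so. A subject whose visits fall near a boundary may occasionally have two in one window and none in the next.

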3.6.2. Selection of Data in the Event of Multiple Records in a Window

Depending on the statistical analysis method, single values may be required for each analysis window. For example, change from baseline by visit usually requires a single value per visit, whereas a time-to-event analysis would not require 1 value per analysis window but rather 1 value for the study. Unless otherwise noted throughout the rest of this document, when a single value is needed, the following rule(s) will be used:

- If more than 1 assessment occurs during the same nominal visit, select the record closest to the nominal day for that visit.
- If there are 2 assessments that are equidistant from the nominal day, the data of the assessment after the scheduled study day will be used.
- The last measurement will be used if multiple measurements are all taken on the same day.

4. SUBJECT DISPOSITION

4.1. Subject Enrollment

A listing of all subjects in the FAS will be generated to describe site, subject number, first and last IDELA dosing dates, treatment group, the reason for discontinuing study treatment, and the reason for discontinuing study. The site summary will be based on the original site ID from Study GS-US-312-0116.

A by-subject listing for subjects who were screened but not treated in Study GS-US-312-0117 will be listed separately.

4.2. Disposition of Subjects

A summary of subject disposition will be provided for the FAS.

Study treatment disposition will present the number of subjects who:

- were treated in Study GS-US-312-0116
- completed/discontinued treatment in Study GS-US-312-0116 and were not treated in Study GS-US-312-0117
 - met primary study endpoint according to the investigator
 - discontinued study drug with summary of reason for discontinuation
- were treated in Study GS-US-312-0117
- has treatment ongoing in Study GS-US-312-0117
- completed/discontinued treatment in Study GS-US-312-0117
 - met primary study endpoint according to the investigator
 - discontinued study drug with summary of reason for discontinuation

Study disposition will present the number of subjects who:

- were randomized in Study GS-US-312-0116
- completed/discontinued Study GS-US-312-0116 and were not enrolled into Study GS-US-312-0117
 - met primary study endpoint according to the investigator
 - discontinued study with summary of reason for discontinuation

- enrolled into Study GS-US-312-0117
- are ongoing in Study GS-US-312-0117
- completed/discontinued Study GS-US-312-0117
 - met primary study endpoint according to the investigator
 - discontinued study with summary of reason for discontinuation

Long-term follow-up disposition will present the number of subjects who:

- entered long-term follow-up
- completed long-term follow-up
- are ongoing with long-term follow-up
- discontinued the long-term follow-up with summary of reasons for discontinuation

The denominator for the percentages of subjects in each category will be the number of subjects in the FAS. No inferential statistics will be generated.

